5.3.8.4.2 Non-cutaneous SCC

A head and neck examination must be performed by the treating physician or other qualified physician at baseline and during the study for all patients enrolled. The head and neck examination will consist of at least a visual inspection of the oral mucosa and lymph node palpation. This will be done at Screening/Baseline (anytime up to 28 days prior to Day 1), every 12 weeks while the patient is on study, when the patient discontinues vemurafenib unless done within the prior 12 weeks, and at the Safety Follow-Up Visit 28 (\pm 5) days after discontinuing study drug and at 6 months following study drug discontinuation or prior to the initiation of another anti-neoplastic therapy (whichever occurs first). For patients with sustained clinical benefit from continued vemurafenib whose visit frequency is lessened to every 2 cycles at Cycle 13 or beyond, head and neck exams may be performed every 16 weeks to coincide with visit cycles. Any suspicious findings will be referred to an appropriate specialist.

A CT scan of the chest is required for non-cutaneous SCC screening and surveillance for all patients. MRI may be used if a CT scan is contra-indicated for the patient. Because radiologic assessments for tumour burden are a standard requirement for patients with solid tumours, it is not necessary to perform a separate chest CT/MRI. Instead, the same (routine tumour assessment CT/MRI) should suffice for monitoring of non-cutaneous SCC as well for solid tumour patients only. However, chest CT for the evaluation of SCC are required at a minimum of every 6 months for each patient and at 6 months following study drug discontinuation or prior to the initiation of another anti-neoplastic therapy (whichever occurs first). CT scans are not required at 28 days post-discontinuation visit for patients who have discontinued due to CT-documented progression of disease under study.

Pelvic examinations for women (with special attention to cervix) and anal examinations for all patients will be performed at baseline and the end of the study. The pelvic examination should include a complete external and internal examination (internal examination of uterine cervix may include a Pap smear, which would be a decision of the investigator). The anal examination should include external examination, digital anorectal examination and anoscopy or proctoscopy. However, if in opinion of the investigator the presence of "abnormal lesions including SCC" can be excluded by the external inspection and the manual examination, this is acceptable. However, if the presence of a lesion is suspected, an anoscopy or proctoscopy are recommended.

5.3.8.5 Electrocardiographic assessments

Prolongation of the corrected QT (QTc) interval (change from baseline) has been reported in vemurafenib clinical trials. As a result of these findings, mandatory ECG assessments, with a focus on QTc interval, will be conducted during the Screening Period, 4 weeks after starting vemurafenib treatment, every 4 weeks for the next 3 months, every 12 weeks thereafter during the Treatment Period, at the End of Treatment Visit, and at the Safety Follow-Up Visit. The following parameters will be collected: heart rate, PR interval, QRS duration, QT and QTc intervals, and ECG findings.

Please refer to Section 6.2.1 and 6.3.3 for dose modifications guidelines (for vemurafenib monotherapy and the combination of vemurafenib and cetuximab) to minimize the risk of ventricular arrhythmia in patients with metastatic melanoma treated with vemurafenib.

5.3.8.6 Photosensitivity

Photosensitivity has been reported in patients treated with vemurafenib in clinical trials. The majority of cases were mild or moderate in severity. All patients should be advised to avoid sun exposure and/or wear protective clothing with sun block and lip balm (minimum of SPF 30, re-applied every 2 to 3 hours) during vemurafenib treatment and for at least 5 to 10 days after study drug discontinuation.

5.3.8.7 Pancreatitis

The Sponsor recommends that workup of any suspected case of pancreatitis should include serum amylase and lipase testing in addition to other appropriate testing (e.g. CT of the abdomen).

5.4 LABORATORY ASSESSMENTS

Samples for haematology, serum biochemistry, and pregnancy will be analysed at the study site's local laboratory as part of regular safety assessments. Protection of patient confidentiality (See [Section 16](#)) will extend to any data generated from the assaying of these samples.

Normal ranges for the study laboratory parameters must be supplied to Roche before the study starts. Changes to the normal ranges during the course of the study should be notified to Roche as soon as possible.

Laboratory assessments will be performed at screening/baseline, at each every 28-Day visit and at the end of the study visit.

5.4.1 Safety Laboratory Assessments

Haematology and biochemistry will be done as part of regular safety assessments. Specifically:

- Haematology: Haemoglobin, haematocrit, white blood cell count (WBC), absolute neutrophil count (ANC), and platelet count
- Biochemistry: amylase, lipase, glucose, blood urea nitrogen (BUN), creatinine or creatinine clearance (CrCl), sodium, potassium, calcium, magnesium, bicarbonate (if routinely performed on venous blood samples), total bilirubin with fractionation into direct and indirect bilirubin (if total bilirubin is elevated; if one component is available, the other component can be calculated), alkaline phosphatase, and AST (SGOT), ALT (SGPT)
- Serum pregnancy test in all women of child-bearing potential at screening (within 7 days prior to first administration of vemurafenib).

5.4.2 Pharmacokinetic Assessments

For all newly enrolled patients in all cohorts, mandatory blood samples will be taken during Cycle 1 (Day 1 and Day 15) and Cycles 2 – 4 (Day 1) to explore the PK characteristics of vemurafenib. Samples will be taken pre-dose and 2-4 hours post-dose of the morning dose on the corresponding days (see [Table 9](#)). For the day of the PK assessment, patients should be instructed not to take their morning dose, and to bring their study medication with them to their clinic visit.

Table 9:
PK Blood Draws

Cycle	Day	Blood Volume Required per Sample	Blood Volume Required per Sample
1	1	pre-dose	2 mL
		2-4 hrs post-dose	
	15	pre-dose	
		2-4 hrs post-dose	
	2	pre-dose	
		2-4 hrs post-dose	
3	1	pre-dose	2 mL
		2-4 hrs post-dose	
4	1	pre-dose	2 mL
		2-4 hrs post-dose	

For all PK samples, the date and time of the last dose of vemurafenib should be recorded, along with the actual time of the PK blood draw. The procedures for the collection, handling and shipping of samples for PK can be found in the study's Laboratory Manual.

Collected samples will be destroyed no later than five years after the end of the study.

5.4.3 Exploratory Biomarkers

Optional blood samples for exploratory biomarkers can be collected from any newly enrolled patient in any cohort. Blood samples will be taken at pre-dose of the morning dose of Cycle 1 (Day 1) and Cycle 2 (Day 1), as well as at the Safety Follow-up Visit or at time of disease progression (whichever occurs first), with approximately 10 mL blood being required at each time point (see [Table 10](#)). Any collected samples will be destroyed no later than five years after the end of the study.

For these patients, BRAF V600 mutations in tissue may be correlated to BRAF V600 mutations in plasma and assessed in relation to clinical parameters and clinical outcome. Further exploratory analysis may include, but are not limited to, markers relevant in the pathogenesis, course and outcome of vemurafenib treatment, such as genetic alterations and candidate biomarkers.

Table 10:
Biomarker Samples (Optional)

Cycle	Day	Timing	Blood Volume Required
1	1	pre-dose	10 mL
2	1	pre-dose	
Safety Follow-up Visit or at time of disease progression (which ever happens first)		pre-dose (if applicable)	

The procedures for the collection, handling and shipping of biomarker samples can be found in the study's Laboratory Manual.

6. INVESTIGATIONAL MEDICINAL PRODUCT

6.1 VEMURAFENIB

The formulated drug product vemurafenib is provided as 240-mg film-coated tablets packed in bottles for oral administration. For additional batch-specific instructions and information, vemurafenib will be labelled in compliance with Good Manufacturing Procedures (GMP). The drug label will include the contents, protocol number, batch number, and storage conditions, as well as any required statements that the drug is: "For Clinical Trial Use Only." Patients will be requested to store the vemurafenib at the recommended storage conditions noted on the label out of the reach of children or other cohabitants. For further details, please see the vemurafenib IB.

6.2 DOSE AND SCHEDULE OF VEMURAFENIB

Patients will receive continuous oral doses of vemurafenib 960 mg b.i.d. without scheduled dose interruption starting on Day 1 (except for Part I of Cohort 3b where vemurafenib starts on Day 2 [administered while in hospital], see [Section 6.3](#)) of the Treatment Period until the development of progressive disease, unacceptable toxicity, consent withdrawal, protocol violation endangering the patient's safety, death, reasons deemed by the Investigator, or study termination by the Sponsor.

Vemurafenib is supplied in 240 mg film-coated tablets packed in bottles for oral administration. Patients should be instructed to take four tablets in the morning and four tablets approximately 12 hours later in the evening (total daily dose of 1920 mg [960 mg b.i.d.]) (except for Cohort 3b where vemurafenib dose will be determined by the dose finding phase, see [Section 6.3](#)). Each dose should always be taken in the same manner i.e. either with or without a meal.

If vomiting occurs during the course of treatment, no re-dosing of the patient is allowed before the next scheduled dose. However if a patient forgets to take a dose, it can be taken up to 4 hours prior to the next dose.

If a patient misses a dose (e.g., due to emesis), he or she should be instructed not to take or make up that dose and to resume dosing with the next scheduled dose. Missed doses will not be made up. Patients will be instructed to bring all unused tablets to each study visit for assessment of compliance.

Patients who develop disease progression but, in the opinion of the Investigator, would still benefit from continuing study treatment may continue treatment with study treatment after discussion with the Sponsor.

Patients will be given a dosing exception diary to record the time and date of *missed* study medication doses. Any such data provided by the patient will be transcribed from the diary to the eCRF by the study coordinators.

A 6-week supply of study medication (three 120-tablet bottles) will be given to the patient on Day 1 of the first cycle. From Cycle 2 onwards a 4-week supply of study medication (two 120-tablet bottles) will be given to the patient on Day 1 of each dosing cycle. Patients will be instructed not to open a new bottle until the previous bottle has been finished and to bring their study medication and bottles (used or unused) back to the clinic at the next study visit for reconciliation.

If recruitment is expanded in any cohort (due to promising efficacy seen in Stage II), patients who are part of this expansion will receive the same treatment as patients who were treated in Stage II of that cohort.

6.2.1 Dose Modifications, Interruptions, and Delays for Vemurafenib

Management of symptomatic adverse drug reactions (e.g., arthralgia, fatigue, rash) may require temporary interruption and/or dose reduction of vemurafenib treatment. When needed, dose reduction in 240-mg b.i.d. increments is recommended based on individual safety and tolerability. Up to two dose reductions of vemurafenib will be allowed, i.e., to 720 mg p.o. b.i.d., and then to 480 mg p.o. b.i.d. There will be no dosage reductions or interruptions for skin cancer.

Dose escalation after dose reduction is generally not recommended unless under special circumstances, i.e., increased likelihood of clinical benefit for the dose increase and no safety concerns. This should only be done after discussion with the Sponsor. Dose increases above 960 mg b.i.d. are NOT allowed.

Patients with ECD/LCH have the option of discontinuing vemurafenib treatment after one year, if the investigator considers it to be in the best interest of the patient. Patients can then resume vemurafenib treatment if they become symptomatic or if their scans show worsening of their disease.

Dosage modification criteria should occur as follows (also see Table 11):

**Table 11:
Dose Interruption/Modification Criteria for Vemurafenib**

Toxicity Grade (CTCAE, v4.0) ^a	Vemurafenib dose changes during current treatment period	Dose adjustments for resumption of treatment
Grade 1	100% of starting dosage	100% of starting dosage
Tolerable Grade 2	100% of starting dosage	100% of starting dosage
Intolerable Grade 2		
First appearance	Interrupt until resolved to Grade 0 – 1	Reduce by 240 mg b.i.d.
Second appearance	Interrupt until resolved to Grade 0 – 1	Reduce by 240 mg b.i.d.

Toxicity Grade (CTCAE, v4.0) ^a	Vemurafenib dose changes during current treatment period	Dose adjustments for resumption of treatment
Third appearance	Discontinue permanently	
Grade 3 ^b		
First appearance	Interrupt until resolved to Grade 0 – 1	Reduce by 240 mg b.i.d.
Second appearance	Interrupt until resolved to Grade 0 – 1	Reduce by 240 mg b.i.d.
Third appearance	Discontinue permanently	–
Grade 4		
First appearance	Discontinue permanently or interrupt until resolved to Grade 0 – 1 ^c	Reduce to 50% of starting dosage or reduce to 480 mg b.i.d. if starting dose is 720 mg b.i.d.
Second appearance	Discontinue permanently	–

a. Common Terminology Criteria for Adverse Events, Version 4.0.

b. Treatment interruptions or and/or dose reductions for Grade 3 haematology test abnormalities, except for neutropenia and thrombocytopenia, will be at investigator's discretion.

c. Discontinue permanently if starting dose is 480 mg b.i.d.

Prolongation of the corrected QT (QTc) interval (change from baseline) was observed in a substudy of the NP22657/BRIM-2 phase II trial. As a result of these findings, the following recommendations have been developed to minimize the risk of ventricular arrhythmia in patients with metastatic melanoma treated with vemurafenib:

Avoid combination with other agents with known potential to lead to prolongation of QTc interval, if possible.

ECG monitoring, with a focus on QTc interval, should occur during the Screening/Baseline period, 28 days after starting vemurafenib, every 28 days for the following 3 months, and every 12 weeks thereafter until study drug discontinuation at the End of Treatment Visit, and at the Safety Follow-Up Visit.

If QTc interval exceeds 500 ms or the change from baseline is > 60 ms, vemurafenib treatment should be temporarily interrupted. The Investigator should check electrolytes (K+, Mg++, and Ca++) with a focus on hypokalaemia, correct any electrolyte abnormalities prior to reinstitution of therapy, recheck concomitant medications to insure that none has been implicated in QTc prolongation, and rule out or control other cardiac risk factors (i.e., ischemia). ECG should be monitored weekly until QTc decreases to less than 500 ms, at which point treatment should be reinitiated at one reduced dose level, i.e., from 960 mg b.i.d. to 720 mg b.i.d. If a subsequent increase in QTc to > 500 ms or change from baseline is > 60 ms is observed, vemurafenib may be reduced to 480 mg b.i.d.

Vemurafenib should be permanently discontinued if a QTc increase meets both criteria of > 500 ms and > 60 ms change from pre-treatment values or if QTc > 500 ms or change from baseline > 60 ms is observed on two separate prior occasions.

If a patient's study dose has been interrupted for > 4 weeks due to an AE the patient will be considered to have discontinued from the study. However, a temporary discontinuation of drug

for up to 4 weeks is allowed in case of tumour surgery or other procedures for safety reasons or in the best patient interest, or elective procedures in the best patient interest.

For patients required to have tumour surgery, radiotherapy or other procedures, treatment with vemurafenib must be interrupted prior to these procedures. The treating physician must contact the Sponsor for guidelines as when study drug is to be stopped and re-started after the procedure.

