3.1.2 Rationale for Dose Selection

3.1.2.1 Rationale for the starting doses of vemurafenib (Cohort 1-7, excluding Cohort 3b)

The dose of vemurafenib at 960 mg b.i.d was identified in the phase I dose-finding study PLX 06-02 and is established as the recommended dosage for phase II and III trials (see [Section 1.2.4](#)) for the treatment of melanoma. It is presumed that a similar dosage would be effective in other types of cancers harbouring the same BRAF V600 mutations.

3.1.2.2 Rationale for the starting doses of vemurafenib and cetuximab in combination (Cohort 3b)

The loading dose of cetuximab will be 300 mg/m² given intravenously (IV) followed by a weekly IV dose of 200 mg/m² (see [Appendix 1](#) for body surface area calculation). These doses are respectively 75% and 80% of the registered doses as single agent in second or third line for advanced CRC.

Vemurafenib: the starting dose will be 720 mg b.i.d. This is 75% of the registered dose in melanoma when given as single agent.

These starting reduced doses will be explored for safety reasons as vemurafenib and cetuximab will be administered concomitantly.

Doses will be escalated according to a standard 3+3 dose-escalation design (see [Section 6.3.1](#)).

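### Table 11 keys its Grade 4 rule and footnote c to an undefined starting dose, so the stop at 480 mg b.i.d. never applies on the protocol's own usage; its 240 mg steps can also pass below the 480 mg floor

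*Protocol*

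**What the plan says.** All of this is in the Protocol.

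- **Table 11 (Section 6.2.1), first Grade 4 event.** The site may stop vemurafenib for good, or interrupt until the toxicity has resolved to Grade 0–1. The resumption column then reads "Reduce to 50% of starting dosage or reduce to 480 mg b.i.d. if starting dose is 720 mg b.i.d". Footnote c, attached to the interruption option, reads "Discontinue permanently if starting dose is 480 mg b.i.d".
- **Table 11, Grade 1 and tolerable Grade 2.** The dose is "100% of starting dosage".
- **Table 11, intolerable Grade 2 and Grade 3.** The first and second appearance of each grade takes 240 mg b.i.d. off the dose; the third stops treatment. Appearances are listed separately by grade, and the table gives no lowest dose.
- **Text of Section 6.2.1.** "Up to two dose reductions of vemurafenib will be allowed, i.e., to 720 mg p.o. b.i.d., and then to 480 mg p.o. b.i.d". On going back up: "Dose escalation after dose reduction is generally not recommended unless under special circumstances". The QTc rule in the same section restarts treatment from the dose the patient was on: "at which point treatment should be reinitiated at one reduced dose level".
- **Initial doses.** In the monotherapy cohorts, "Patients will receive continuous oral doses of vemurafenib 960 mg b.i.d. without scheduled dose interruption" (Section 6.2). For Cohort 3b, Section 3.1.2.2 says "the starting dose will be 720 mg b.i.d". Section 6.3.1 lists levels 1, 2, 1A and 2A at 720 mg b.i.d. and levels 3 and 3A at 960 mg b.i.d.
- **Reach of the table.** Section 6.3.3 sends Cohort 3b to Section 6.2.1 and Table 11 for vemurafenib reductions.

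**The concern.** Footnote c is a safety stop. It is meant to keep a patient from resuming after a Grade 4 event when no lower permitted dose is left. It is written in terms of a starting dose of 480 mg b.i.d., and nobody in this trial starts at 480 mg. If a site reads the term as Section 3.1.2.2 uses it, the stop is empty and the Grade 4 row returns the dose at which the life-threatening event occurred.

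The second issue is a mismatch between table and text. The text names 720 and then 480 mg, which is the ladder for a patient who began at 960 mg. Table 11 also governs patients who began at 720 mg, and its subtraction rule has no floor. A site working from the table can arrive at 240 mg b.i.d., a dose the text does not allow.

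At stake is what a site does with a patient at 480 mg who has a further toxicity.

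**Working it through.** No sample size, power or error rate is involved. The check is to follow the table's rules from each possible dose.

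**Inputs.** Initial doses are 960 mg b.i.d. (Section 6.2; Cohort 3b levels 3 and 3A) or 720 mg b.i.d. (Section 3.1.2.2; Cohort 3b levels 1, 2, 1A and 2A). The lowest dose in the text is 480 mg b.i.d., with two reductions allowed (Section 6.2.1). The step and Grade 4 rules are those of Table 11.

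**1. First Grade 4 event, treatment interrupted rather than stopped.** The rule gives 0.5 × 960 = 480 mg when the starting dose is 960 mg, 480 mg when it is 720 mg, and discontinuation when it is 480 mg.

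| Initial dose | Dose at event | Term read as initial dose | Term read as dose at event |
|---|---|---|---|
| 960 | 960 | 480 | 480 |
| 960 | 720 | 480 | 480 |
| 960 | 480 | 480 (480 − 480 = 0, no reduction) | discontinue (footnote c) |
| 720 | 720 | 480 | 480 |
| 720 | 480 | 480 (no reduction) | discontinue (footnote c) |

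The two readings differ only for a patient already at 480 mg. Footnote c comes into play only in the last column.

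**2. Grade 1 or tolerable Grade 2 in a 960 mg starter now on 480 mg.** Read as initial dose, the table gives 960 mg; read as dose at event, 480 mg. The first result conflicts with the text on re-escalation, which is evidence that the dose at the event is meant.

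**3. The 240 mg steps.** These do not depend on how the term is read.

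- 960 mg starter, one grade only: 960 → 720 → 480 → stop. This agrees with the text.
- 720 mg starter, one grade only: 720 → 480 → 240 at the second appearance. This is below the floor although only two reductions have been made.
- 960 mg starter, first Grade 4 and then first Grade 3: 960 → 480 → 240. This too is below the floor within two reductions.
- 960 mg starter, intolerable Grade 2 twice and then Grade 3: 960 → 720 → 480 → 240. Here the limit of two reductions is exceeded as well.

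**4. Check of the remedy.** With the dose at the event as the reference and a stated floor, Grade 4 gives 960 → 480, 720 → 480 and 480 → discontinue. Each path in item 3 that reached 240 mg ends in discontinuation instead.

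**The case against.** The best defence is that the section, read as a whole, already gives the right answer.

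- **The Grade 4 row.** A patient on 480 mg cannot *reduce* to 480 mg, permanent discontinuation is listed first, and a reading that empties a safety footnote is not the natural one. This stands in part. It makes the dose at the event the probable intent, and it rules out saying that the protocol directs such patients to resume unchanged. It does not supply a definition, and the one place that explains the term, Section 3.1.2.2, points the other way.
- **The floor.** The text before Table 11 says what is allowed and can be read as governing the table. That is fair for the usual 960 mg single-grade path and for sequences needing a third reduction. It leaves open a 720 mg starter, for whom the text's ladder was not written and whose second reduction under the table is to 240 mg.
- **Re-escalation.** A reader might infer that the Grade 1 row orders a reduced patient back to 960 mg. It does not: the text discourages this and requires discussion with the Sponsor. The row only needs wording that agrees with the text.
- **Cetuximab.** A reader might infer that Table 13 has the same fault. There the term reads naturally as the assigned weekly dose. Holding 75% after a second intolerable Grade 2, with a stop at the third, is a workable rule, and changing it would be a new clinical choice.
- **Frequency.** A reader might try to estimate how many patients would be affected from the melanoma counts in Section 1.3.5.2. Those counts give neither the joint occurrence nor the order of reduction to 480 mg and a Grade 4 event, so they support no estimate.

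**Conclusion.** The point holds as a minor patient-safety and clarity correction to Table 11. On the protocol's own usage of the term, footnote c can never apply, and a patient at 480 mg b.i.d. who is not discontinued has 480 mg as the resumption dose after a first Grade 4 event; on the probably intended reading that patient stops. Independently, the 240 mg steps contradict the 480 mg limit for a 720 mg starter in Cohort 3b and for a 960 mg starter in mixed-grade sequences.

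The first part assumes that a site reads the term as Section 3.1.2.2 uses it and does not choose permanent discontinuation. The mixed Grade 2 and Grade 3 paths assume that appearances are counted separately by grade, as the rows are laid out.

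A reader might infer a threat to the response rate or to the Cohort 3b dose decision. The documents do not support that: the dose-limiting toxicity criteria and escalation rules (Section 6.3.2) are set out separately from Table 11, and no effect on endpoints or the recommended dose follows from this wording.

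**What to change.** In Table 11:

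1. Replace *starting dose* and *starting dosage* with *dose at the time of the event* in the Grade 1, tolerable Grade 2 and Grade 4 rows and in footnote c. Grade 4 then reads: 960 to 480 mg, 720 to 480 mg, 480 mg discontinue.
2. Add one line: *Vemurafenib is discontinued if a reduction below 480 mg b.i.d. would be needed.*

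Table 13 needs no dose change on this account.

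The cost is a few words and one added sentence in an amendment, with no extra patients, visits or procedures. The real trade-off is that a patient at 480 mg b.i.d. who needs a further reduction can no longer resume vemurafenib. This will be felt soonest in Cohort 3b patients who start at 720 mg, because they have only one step before the floor.
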